- Comparison of the following variables between the groups: granulation tissue integrity including hypergranulation state, time to close, flap/graft take, dehiscence, and reoccurrence.

Objective 2

To compare bacterial load, quantitative cultures, and clinical infections in wounds treated with NPWT PRO compared to wounds treated with NPWT PRO with simultaneous irrigation.

H1: Bacterial load measured with quantitative polymerase chain reaction (qPCR) will be progressively lower with continuous irrigation.

H2: Patients treated with simultaneous irrigation and NPWT PRO will have fewer infections defined by qPCR and clinical criteria.

Primary Endpoint:

- Comparison of reduction in bacterial load in wounds treated with NPWT and NPWT with simultaneous irrigation.

Secondary Endpoints:

- Comparison of incidence of infection in wounds treated with NPWT and NPWT with simultaneous irrigation.
- Infection-induced necrosis
- Infection reoccurrence post-closure

Objective 3

Assess changes in molecular markers associated with wound healing and regeneration of healthy tissue.

H1: NPWT PRO with simultaneous Irrigation will improve the levels of growth factors, cytokines, and other molecular markers over NPWT PRO alone.

H2: Negative pressure wound therapy will drive molecular changes in growth factors and other cytokines associated with regeneration of healthy tissue.

Primary Endpoint:

- To compare changes in genes and other molecular markers associated with wound healing between wounds treated with NPWT and NPWT with simultaneous irrigation.

Secondary Endpoint:

- To compare the addition of simultaneous irrigation on gene expression and expression of molecular markers from baseline.

Objective 4

Quality of Life and Patient Satisfaction Analyses

H1: Patients treated with the NPWT PRO device will show greater patient satisfaction with treatment than those treated with KCI Ultra NPWT therapy.

Primary Endpoints:

- To compare Quality of Life and Patient Satisfaction between patients treated with NPWT PRO versus patients treated with KCI Ultra NPWT therapy.
- To compare Quality of Life and Patient Satisfaction between patients with wounds treated with NPWT PRO versus NPWT PRO + SI.
- Evaluate functional status, using the Short Form 36 (SF36). These will be administered at baseline and at the last study visit.

Subjects and Recruitment

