If evaluation of the clinical indicators suggest the presence of significant bacterial infection of the wound, swab culture, utilizing swab technique [126] will be performed to confirm or reject the presence of significant bacterial infection severe enough to warrant the subject terminated from the study. The swab culture will be performed using a laboratory-provided swab that is pressed down over a 1 cm² area of the wound that is then delivered to the lab for analysis to determine Colony-Forming Units (CFUs) per gram of viable wound tissue and beta-hemolytic Streptococcus per gram of tissue. The findings of a positive or negative swab culture utilizing Levine's technique will be interpreted according to the following criteria:

- Positive culture indicating presence of bacterial infection: $\geq 1,000,000$ Colony-Forming Units (CFUs) per gram of viable wound tissue OR containing beta-hemolytic Streptococcus per gram of tissue at any level.
- Negative culture indicating absence of bacterial infection: $< 1,000,000$ Colony-Forming Units (CFUs) per gram of viable wound tissue OR no beta-hemolytic Streptococcus per gram of tissue at any level.

Tissue specimens will be obtained from the chronic wounds using 1) wound exudate, 2) broad Z-technique, and 3) Levine technique [126]. Acquisition of swab specimens was followed with a wound tissue biopsy. The diagnostic validity of each technique was determined by associating the quantitative culture findings of each swab specimen with the culture findings of concurrent tissue specimen (gold standard). Levine's technique performed best of the three swab techniques in terms of all four validity parameters: sensitivity was, specificity, positive predictive value, and accuracy.

Bio-burden

Bio-burden will be assessed using qPCR to quantify bacterial load from serial tissue specimens. Specific organisms that will be quantified using qPCR are listed in the table below. Bone, soft tissue will be sent to Research and Testing Laboratory (Lubbock, TX) for analysis.

Specific organisms (and two resistance factors) to be quantified using qPCR.			
E. faecalis	E. faecium	S. epidermidis	M. morgani
K. pneumonia	S. aureus	C. striatum	S. haemolyticus
S. agalactiae	S. marcescens	F. magna	S. mutans
S. pyogenes	H. influenzae	P. mirabilis	Vancomycin res.
C. albicans	M. catarrhalis	C. parapsilosis	Methicillin res.
P. aeruginosa	S. pneumoniae	A. baumannii	Total Bioburden

Osteomyelitis

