The inpatient stay and post-operative visits are covered under a 90-day global payment which is inclusive of all procedures, devices, testing and ancillaries associated with the surgical procedure, including NPWT. Subjects’ insurance will not be charged any additional amount for the NPWT devices used in the study. The KCI devices are standard at Parkland; Cardinal is providing their devices. But again, in neither situation would a subject or their third party pay or be charged anything additional.

Survival Analyses Models

The primary analytical method presented in this report is based on a time-to-event strategy using Kaplan-Meier estimates, followed by a log-rank test. This statistical procedure provides a comparison of the distribution of events between the 2 treatment groups. In addition to the event rates calculated for the post-baseline time points, the median time to 100% closure, 75% closure, and 76-100% wound bed granulation will also be calculated. This same methodology will also be used to compare the overall duration of treatment, and within the individual patient subsets defined by their outcome status.

A Cox proportional hazard model will be used to relate time to specific events to various risk factors. The main modeling strategies will look at the time to adverse events with time being measured from the time of surgery or the time of NPWT application until either an adverse event occurs, the patient is considered healed, or the end of the study. Cox proportional hazard model allows the independent variables to be continuous covariates or categorical or binary factors. The type of NPWT treatment will be the main independent variable. We will use multivariate proportional hazard regression analysis methods to investigate what factors are significant for non-healing patients or patients that have complications. Similar to the logistic regression, maximum likelihood estimates of model parameters along with tail probabilities (p-values) and confidence intervals for parameters

will be derived based on asymptotic inferences. For the proportional hazard model the ratio of the hazards for two subjects one with and one without diabetes, given that the subjects have the same values for other parameters can be estimated from the model coefficients. Repeated measures ANOVA and ANOVA will be used to evaluate changes in quantitative cultures and laser Doppler measurements over time and between treatment groups.

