Continuous demographic parameters, such as the patient's age at the time of enrollment, will be summarized for the population using descriptive statistics (N, mean, median, standard deviation, minimum and maximum value, and 95% 2-sided confidence limits) and compared between groups using a 2-sample t-test. Categorical demographic parameters, such as gender, were summarized as a proportion of the intent-to-treat (ITT) population and compared using a 2-tailed Fisher's exact test. Co-morbid risk factors will be summarized for the ITT population by treatment assignment and according to the type of variable (categorical, continuous) and compared between groups. Relative risk will be evaluated using a logistic regression model.

For direct comparisons of the NPWT PRO and KCI Ultra systems, a traditional non-inferiority statistical procedure will be performed. It will be assumed that the efficacy of the NPWT PRO device in wound outcomes is not inferior to the KCI device if it performs within $\pm 10\%$ of the performance of the KCI Ultra system.

Microbial Diversity

Results from the qPCR assessment of bio-burden will be analyzed using standard multivariate approaches. Multivariate differences in bacterial composition among groups will be evaluated using distance based redundancy analysis (dbRDA) [128]. For the dbRDA, distances among samples first will be calculated using unweighted UniFrac distances. UniFrac distances are a robust phylogenetic measure that is useful for comparing microbial communities [129]. An ANOVA-like simulation will then be used to test for group differences.

Facilities

The University of Texas Southwestern Medical Center's Musculoskeletal and Vascular Effectiveness Research Collaboration (MAVERIC) group has 1,200 square feet of dedicated research and clinic space. We have office space for four investigators and seven research coordinators and two nurse coordinators. We have arterial Doppler systems, vibration perception threshold testing equipment and computer workstations. Research patients are seen at the NIH sponsored research center at the University of Texas (5 treatment rooms, laboratory) and the Ambulatory Surgery Center at Parkland Hospital (6 treatment rooms).

- *Human Subjects Research:* The proposed involvement of human subjects, characteristics of the subject population, inclusion/exclusion criteria, and recruitment and consent procedures are described in the Experimental Design and Methods section of this proposal.

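### The Objective 2 bacterial-load endpoint has no clearly assigned quantitative analysis, and the one method named for the qPCR bio-burden data ignores quantity

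*Combined protocol and SAP*

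**What the plan says.** Under Study Objectives and Endpoints, the Objective 2 primary endpoint is "Comparison of reduction in bacterial load in wounds treated with NPWT and NPWT with simultaneous irrigation". Its first hypothesis fixes the measurement: "Bacterial load measured with quantitative polymerase chain reaction (qPCR) will be progressively lower with continuous irrigation". The Bio-burden section agrees: "Bio-burden will be assessed using qPCR to quantify bacterial load from serial tissue specimens". The panel there, captioned "Specific organisms (and two resistance factors) to be quantified using qPCR", ends with an entry for total bioburden.

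The analysis appears in the Biostatistics part, under Microbial Diversity: "Results from the qPCR assessment of bio-burden will be analyzed using standard multivariate approaches". The target stated there is composition: "Multivariate differences in bacterial composition among groups will be evaluated using distance based redundancy analysis (dbRDA"). For that step, "distances among samples first will be calculated using unweighted UniFrac distances", and a simulation test for group differences follows.

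A separate sentence under Survival Analyses Models reads: "Repeated measures ANOVA and ANOVA will be used to evaluate changes in quantitative cultures and laser Doppler measurements over time and between treatment groups". It does not mention qPCR, a log scale, baseline adjustment or non-detects.

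**The concern.** The endpoint is a quantity followed over time, and qPCR was chosen to supply that quantity. The one analysis tied by name to the qPCR results reduces each organism to detected or not detected. An analyst who follows the Microbial Diversity section for Objective 2 could find no difference after a large fall in load and report that irrigation had no bacterial effect. An analyst who sees the problem would have to choose a load model, a scale and a rule for non-detects after the data are in hand.

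Changes of one log matter on the protocol's own account. Its section on Negative Pressure Wound Therapy cites a study in which each log order of colony-forming units went with a 44% delay in healing.

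**Working it through.** The plan gives no effect size, SD, power or alpha for bacterial load, so there is no figure to reproduce. The check covers what the named distance measures, how a test built on it behaves, and whether another sentence of the plan covers the endpoint.

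**1. The distance.** For samples A and B on a tree with branch lengths L, let I equal 1 if any organism below a branch is detected and 0 otherwise. Then

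unweighted UniFrac = Σ L·|I(A) − I(B)| / Σ L·max(I(A), I(B)).

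If A and B contain the same detected organisms, every term in the numerator is 0. Computed on an illustrative 22-taxon tree, falls of 1, 2 and 3 log10 (3 log10 is 1,000-fold, or 99.9%) each gave exactly 0.

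The normalised weighted form replaces I by p, the share of total load below the branch: Σ L·|p(A) − p(B)| / Σ L·(p(A) + p(B)). Dividing every load by the same constant leaves p unchanged, so this distance is also 0 (computed: 0 to rounding).

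**2. Organisms falling below detection.** With an assumed detection limit of 10³, one illustrative sample with 10 detected organisms gave:

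| Fall in load | Organisms still detected | Unweighted distance from start |
|---|---|---|
| 1 log10 | 9 | 0.060 |
| 2 log10 | 8 | 0.097 |
| 3 log10 | 5 | 0.426 |
| 4 log10 | 0 | not computed |

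The distance does respond, but through dropout of organisms. Between two samples with nothing detected, the formula is 0/0.

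**3. Test behaviour.** The protocol enrols 90 subjects at 1:1:1, so 90/3 = 30 per arm. A permutation test on unweighted UniFrac (199 permutations, 5% level) stood in for the planned dbRDA test and was set against a t-test on log10 total load, with 100 replicates. Assumptions, none from the documents: a random 22-taxon tree; each organism present with probability 0.35; mean log10 load 5.5; SD 1 between subjects and 0.8 between organisms.

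| Between-arm reduction | Detection limit | UniFrac test rejects | t-test on log10 load rejects |
|---|---|---|---|
| none | none | 2% | 2% |
| none | 10³ | 6% | 5% |
| 1 log10 | none | 4% | 96% |
| 1 log10 | 10³ | 13% | 93% |
| 2 log10 | none | 7% | 100% |
| 2 log10 | 10³ | 82% | 100% |

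The Monte Carlo standard error is √(0.05 × 0.95/100) ≈ 2 points near 5% and √(0.82 × 0.18/100) ≈ 4 points at 82%. The t-test used total load before the detection limit was applied, so its 93% and 100% do not include any loss from non-detects.

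**4. Does the ANOVA sentence cover qPCR load?** The documents point both ways.

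- Against: the statement of Objective 2 lists bacterial load and quantitative cultures as separate items.
- For: the Schedule of Events uses the term qPCR cultures.
- For: under Swab Culture, a colony count is made only when clinical signs suggest significant infection. That gives no regular series for a repeated measures analysis, whereas qPCR is run on serial tissue.

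If the ANOVA covers only the swab counts, it describes a selected subset and leaves the endpoint without a quantitative analysis. If it covers qPCR, the scale, the baseline adjustment and the handling of non-detects are still unstated.

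**5. The panel.** Six rows of four give 24 entries: 19 bacteria + 2 yeasts + 2 resistance factors + 1 total = 24. The last three entries have no place on a phylogenetic tree. The plan does not say which entries enter the distance.

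**The case against.** The dbRDA stands under Microbial Diversity, is described as a comparison of composition, and is nowhere called the test of load reduction. Presence/absence is an accepted basis for a composition distance. It also has some relevance to the aim stated under Innovation of learning how long eradication takes. The ANOVA sentence may already supply the quantitative analysis. Load is not among the primary outcomes listed under Study Groups and Design, and the qPCR values are collected whatever the SAP says.

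Most of this stands, and it rules out several stronger readings that a reader might infer:

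- That the planned test cannot detect a load reduction. With a detection limit it rejected in 82% of simulated replicates at 2 log10.
- That the plan makes UniFrac the load test, or has no quantitative analysis at all. The first is not stated, and the ANOVA sentence leaves the second open.
- That resistance factors, the total or yeasts will be put on the tree. The text limits the dbRDA to bacteria and is silent on the other entries.
- That another composition distance is required. That choice is a preference, and weighted UniFrac shares the blindness to a uniform fall.

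The objection does not show which analysis belongs to the Objective 2 primary endpoint. The reader has to guess what quantitative cultures means, and the only method attached to qPCR by name does not use the quantities.

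**Conclusion.** The point holds as a gap in assignment. The Objective 2 primary endpoint is qPCR load, the one analysis expressly named for qPCR bio-burden does not measure load and can miss large reductions, and the ANOVA that might fill the gap is ambiguous.

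The zero distance for a uniform fall with the same organisms detected is exact and needs no assumption. The rejection rates (4% to 13% against 93% to 96% at 1 log10; 7% to 82% against 100% at 2 log10) are illustrative. They depend on the assumed tree, prevalence, SDs and detection limit, and on all 30 subjects per arm having a later sample. The Schedule of Events ties later samples to further inpatient surgery, so fewer may be available. The wide range at 2 log10 shows that the UniFrac test's sensitivity turns on a detection limit for which the plan gives no value.

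This should be corrected before the qPCR data are analysed. It does not affect the wound-healing outcomes or the sample size, which rests on closure proportions.

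**What to change.** In the Biostatistics part:

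1. Name log10 total bioburden by qPCR as the Objective 2 primary analysis variable. Compare PRO with PRO plus simultaneous irrigation in a model adjusted for Day 0 log10 load.
2. State which later inpatient samples enter the model, and give a rule for non-detects.
3. Say that this model replaces, or specifies, the repeated measures ANOVA sentence for qPCR, and say what quantitative cultures refers to.
4. Keep the dbRDA as a secondary composition analysis limited to the 19 bacterial taxa, with the resistance factors, the total and the yeasts left out of the tree. Changing its distance is optional. Weighted UniFrac would not answer the load question.

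The cost is SAP wording and one further model on Day 0 and later inpatient samples that the protocol already collects. No new samples, visits or subjects are needed.
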